6.1 EPIDEMIOLOGY OF URINARY TRACT MALIGNANCIES IN DIABETES PATIENTS

Based on data from the national cancer registries throughout the Nordic countries, the crude incidence rates (IRs) for urinary tract malignancies (bladder and renal cancers) in the Nordic countries in 2013 was calculated as 43.0 per 100,000 person-years (PY) for the total population and 82.8 per 100,000 PY for individuals over 40 years of age (Table 1) [[R15-4873](#)]. As the study population consists of T2D patients who initiate second- or third-line treatment, the majority of the patients are expected to be over 40 years old. The crude incidences of bladder cancer in the UK, as reported through cancer registries to GLOBOCAN, were lower, as compared to the Nordic countries, but rates for renal cancer were comparable (Table 1) [[R15-4860](#)]. In both regions, incidences are higher among men.

Table 1 Crude incidence rates per 100,000 person-years for urinary tract cancers, Nordic countries 2013 and the UK 2012

	Nordic Countries			The UK		
	Male	Female	Total	Male	Female	Total
Total Population						
Bladder	43.7	14.6	29.1	20.5	7.6	14
Renal	17.6	10.2	13.9	19.6	11.5	15.5
UT (bladder + renal)	61.3	24.9	43.0	40.1	19.1	29.5
Age ≥ 40 years						
Bladder	87.3	27.7	56.5	47.2	16.5	31.2
Renal	34.3	18.8	26.3	44.0	23.9	33.5
UT (bladder + renal)	121.6	46.5	82.8	91.3	40.4	64.7

Source: R15-4873; R15-4860

UK=The United Kingdom; UT=Urinary tract

T2D seems to be associated with an increased risk of several types of cancer when compared to the general population. Reviews of recent studies and meta-analyses indicate increased risks for liver, pancreas, colorectal, kidney, bladder, endometrial and breast cancers, as well as non-Hodgkin's lymphoma in patients with T2D [[R10-6494](#), [R12-2439](#), [R12-0469](#)]. A population-based cohort study on patients hospitalized with T2D diagnoses in Denmark showed a higher risk of kidney cancers (with the standardized incidence ratios (SIRs) of 1.4 (95% confidence interval (CI); 1.2–1.6) in males and 1.7 (95% CI; 1.4–1.9) in females) and liver cancers (with the SIRs of 4.0 (95% CI; 3.5–4.6) in males and 2.1 (95% CI; 1.6–2.7) in

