8.3.3 Covariates

Variables potentially associated with urinary tract cancers, such as socio-demographic variables including age, sex, socioeconomic status, body mass index, smoking and alcohol consumption, laboratory measurements, concomitant medications, comorbidities, and duration of look-back period (see [Section 6.1](#)), will be identified for study participants as recorded prior to the index date (see [Annex 6](#) for list of covariates to be included in the study). With the exception of exposure to toxic chemicals such as arsenic, known risk factors for urinary tract cancers are captured in CPRD and the national registers from Sweden and Finland.

Study participants will also be classified by indicator variables on the calendar time of cohort entry (by quarter) whether the index treatment (empagliflozin, or DPP-4 inhibitor) was added to existing medication (adding on), or if the index treatment was initiated as a replacement for another antihyperglycemic medication (switching to empagliflozin, or DPP 4 inhibitor), and whether this treatment was received as monotherapy or as dual or triple combination therapy. A variable indicating whether or not patients were receiving insulin at the index date will also be created.

The confounding due to covariates in this section are to be accounted for at minimum by design or analysis when estimating the risk of urinary tract cancers with the defined

The examples of covariates in Table 4 describe the comorbidities, treatment history, and socio-demographic variables that will be considered for inclusion. These variables along with times of occurrence/diagnosis of comorbidities, times of prescription/dispensing of drugs and times of recording of the socio-demographic variables in combination with the exposure and outcome variables define the minimal required dataset.

Table 4

Baseline covariates to be considered for inclusion alternatively or simultaneously in primary, secondary, and further analyses

Covariate	Exact matching	PS matching	Stratification	
Database variable (for CPRD only) ¹				
Patient database (Aurum vs GOLD)	Yes	Yes		
Socio-demographic variables				
Age	Yes	Yes	Yes	
Sex	Yes	Yes	Yes	
Socioeconomic status (if available)		Yes		
Calendar year of index date		Yes		
Duration of look-back period		Yes		
Insulin concomitant (or cumulative duration of) use		Yes	Yes	
Other oral antihyperglycemic medication use		Yes		
Comorbidities				

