8	13-APR-2022	6.7.2	The description of the Crude, base and fully adjusted models was aligned with the protocol. Additional criteria for selecting covariates for adjustment were introduced.	The incidence rates observed in the 5 th interim report suggest there will be few events for outcomes such as renal cancer. With few events, it will not be possible to build a model including all selected confounders. The chosen method limits the covariates of the model to confounders which are not balanced in the matched sample.

Proprietary confidential information © 2024 Boehringer Ingelheim International GmbH or one or more of its affiliated companies

9	13-APR-2022	Multiple	Pooled analysis of individual level data are replaced with aggregate level data meta-analyses. Pooled IRs will be estimated by pooling aggregate level data. Pooled HRs will be estimated using meta-analysis methods.	Individual level data from Finland and Sweden cannot be pooled together due to new regulations in the storage and use of individual level data in Sweden and Finland.
10	13-APR-2022	Multiple	Covariate selection criteria were added to mitigate the effect of missing data as well as potential Cox model convergence failures due to small number of events.	Observed incidence rates in interim report 5 suggests that there will be very few events observed for some outcomes such as renal cancer. In addition, stratified analyses that were to be carried out on pooled individual data will now be carried out at the single country level. It is therefore necessary to plan for possible convergence failure for some Cox proportional hazards models.

Proprietary confidential information © 2024 Boehringer Ingelheim International GmbH or one or more of its affiliated companies

12	13-APR-2022	Multiple	
Specified algorithms for inclusion and exclusion criteria
 
Redefined the AT and ITT exposure definitions as two time-fixed variables
 
Adjusted the definitions of time at risk, latency period and treatment discontinuation.
 
Specified algorithms for drug exposure definitions.
 
Removed stratification of metformin use from stratified analyses. (Analyses in study groups have covered subgroups by metformin use)
 
Changed some covariates from time-dependent to time-fixed
	Modifications made to clarify the expected analyses for programmers.

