6.5.2. Matching method

For matching the full cohort, concomitant use of metformin at index date will be an exact matching variable.

Matching will be carried out in several rounds to achieve the highest possible matching ratio given the available data in each country (up to 1:3 matching). In the first round of matching, for each empagliflozin initiator i_E with index date T_{i_E} , all individuals initiating DPP-4 inhibitors within 3 months (90 days) before or after T_{i_E} and with the same status of concomitant metformin use at T_{i_E} will be eligible as comparators. For UK CPRD data, only individuals from the same database (GOLD or Aurum) as the empagliflozin initiator will be considered as eligible comparators. Of these, the individual with the closest propensity score(s) to that of i_E within a predefined propensity score interval will be selected (Greedy matching method). In case of ties, the selection will be made randomly. After each round of selection, the selected comparators are then removed from the pool of possible comparators for further selection (sampling without replacement) [5].

The predefined propensity score interval will be calculated based on the standard deviation of the logit of propensity score δ multiplied by a coefficient k . The value of the coefficient k will be initially set to 0.2, i.e. using a caliper of 0.2 standard deviations (i.e. 0.2 δ). The coefficient k will then be calibrated to ensure at least 99% of empagliflozin initiators have matches from initiators of DPP-4 inhibitors after the first round of propensity score matching [6]. The same calibrated matching caliper $k\delta$ used in the first matching round will be reused in the second and third matching rounds.

Matching by time-period, based on index dates, enables better control of time-varying confounders including changing prescription patterns for empagliflozin and potential confounding. In case there is a strong time bias in the number of matches per empagliflozin user (e.g., initiators in early years have more matches than initiators from later years), a relaxation of the criteria for matching within time-period will be considered. In addition, the criteria for calibrating coefficient k may be modified if the data does not allow matching of 99% of empagliflozin initiators.

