All continuous variables will be described using standard statistical measures, i.e. range, mean, standard deviation, median, first and third quartile. All categorical variables will be summarized with absolute and relative frequencies. The standardized differences and p-values for the statistical tests will be also reported.

Results will be reported in 4 tables similar to Table 18.

Standardized difference < 10% will be used as indicator of satisfactory distribution balance after matching [8]. Variables with standardized difference larger than 10% might still exist. The unbalanced variables will be considered as potential confounders and included in the adjustment of Cox's PH model, as described in the comparative analysis (Section 6.7.2). In case a substantial amount of variables remain unbalanced, the PS matching procedure will be re-evaluated by, for example, reducing the caliper width.

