6.7.2. Comparative analysis

Hazard ratios (HRs) for the outcomes defined in Table 8 will be estimated for PS matched cohorts using Cox's PH model with time-varying covariates, if model pre-requisites are fulfilled. HRs will be presented along with 95% CIs. Proportional hazards assumptions for time-fixed exposure variables will be assessed for each model by plotting scaled Schoenfeld residuals.

The comparative analyses will be performed separately for the matched full cohort and matched metformin-user cohort.

Crude model

Crude HRs are calculated using a Cox PH model with as-treated exposure (as defined in Section 5.1.7) as the only included variable.

HRs estimated using the crude model will be presented along with 95% CIs. A table template for the result is given in Table 23. Analysis will be performed separately for each country.

Crude HRs with 95% CIs will be collected from all study countries to carry out meta-analyses as described in Section 6.7.3.2. Results will be reported as in Figure 8.

Base model

Based on the crude model, the base model will be further adjusted with the unbalanced covariates at index date (standard difference $\geq 10\%$) among the variables included in the propensity score model (Section 6.6). The inclusion of adjusting variables will be considered based on data availability as described in Section 10.

HRs estimated using the base model will be presented along with 95% CIs. A table template for the result is given in Table 24. Analysis will be performed separately for each country. HRs with 95% CIs estimated using base model will be collected from all study countries to carry out meta-analyses as described in Section 6.7.3.2. Results will be reported as in Figure 8.

Adjusted model

The base model will be further adjusted with selected time-dependent variables. The following time-dependent variables will be initially considered for inclusion (as detailed in Section 9) in the adjusted Cox's PH model:

- HbA1c value (as defined in Table 11)
- Kidney or genitourinary stones (as defined in Table 13)
- UTI or pyelonephritis (as defined in Table 13)
- Ever exposed to insulin (as defined in Table 14)
- Ever exposed to metformin (as defined in Table 14)

Proprietary confidential information © 2024 Boehringer Ingelheim International GmbH or one or more of its affiliated companies

- Ever exposed to other glucose lowering medication (as defined in Table 14)
- Ever exposed to GLP-1 drugs (as defined in Table 14)

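### Age and sex enter the primary Cox models only if they fail the 10% balance rule; always including them would be a free improvement

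*SAP*

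**What the plan says.** **Matching.** SAP 6.5.2: "For matching the full cohort, concomitant use of metformin at index date will be an exact matching variable". The other restrictions there are an index date within 90 days and, in the UK, the same CPRD database. Neither age nor sex is matched exactly. Both are in SAP Table 11, whose variables SAP 6.5.1 lists as considered for the PS model.

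**Balance.** SAP 6.6.2: "Standardized difference < 10% will be used as indicator of satisfactory distribution balance after matching".

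**Outcome models (SAP 6.7.2).** The crude model contains exposure alone. For the next step, "the base model will be further adjusted with the unbalanced covariates at index date", drawn from the variables in the PS model. After that, "The base model will be further adjusted with selected time-dependent variables". Nine are listed: HbA1c, stones, urinary tract infection and six ever-exposed drug indicators. Age and sex are not among them.

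**Reason given.** SAP section 3, change 8, expects few events for outcomes such as renal cancer, and adds: "The chosen method limits the covariates of the model to confounders which are not balanced in the matched sample".

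**Protocol.** Table 4 marks age and sex for exact matching, PS matching and stratification, under the title "Baseline covariates to be considered for inclusion alternatively or simultaneously in primary, secondary, and further analyses". Its footnote 4 reserves model adjustment for covariates left unbalanced by PS matching.

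**The concern.** A standardized difference measures imbalance only. The confounding that remains is the imbalance multiplied by the covariate's effect on the outcome, so a single cut-off treats a weak predictor and a strong one alike. Sex is a strong predictor here. On Table 1 the protocol remarks: "In both regions, incidences are higher among men". For Nordic bladder cancer at age 40 and over, the rates per 100,000 person-years are 87.3 in men and 27.7 in women, a ratio of 3.15.

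If every baseline covariate passes at 10%, the base model reduces to the crude model and PS matching alone carries the control of age and sex. Any residual imbalance then goes into the pooled HR. If channelling runs the same way in all three countries, pooling does not remove it. In a safety study either direction matters, because the bias could create a signal or hide one.

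**Working it through.** The plan states no figure for residual confounding, so there is none to reproduce. The check bounds what the 10% rule can let through.

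**Inputs**
- Rates at age 40 and over, men / women (protocol Table 1): Nordic bladder 87.3 / 27.7, Nordic urinary tract 121.6 / 46.5, Nordic renal 34.3 / 18.8; UK bladder 47.2 / 16.5, UK urinary tract 91.3 / 40.4.
- Minimum detectable HR in the meta-analysis (protocol Table 9): 1.37 for urinary tract cancer, 1.47 for bladder cancer.
- Assumed, because the documents do not give them: 60% men; SD of age 9–11 years; cancer rate rising 4–8% per year of age; 80% power behind Table 9.

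**Sex at a standardized difference of 9.9%.** With the SAP 6.6.2 formula and p0 = 0.60, solving (p1 − p0) / √{[p1(1 − p1) + p0(1 − p0)] / 2} = 0.099 gives p1 = 0.648, a gap of 4.8 points. The bias factor is the ratio of the two sex-weighted rates.
- Nordic bladder: (0.648 × 87.3 + 0.352 × 27.7) / (0.60 × 87.3 + 0.40 × 27.7) = 66.32 / 63.46 = 1.045
- Nordic urinary tract: 95.17 / 91.56 = 1.039
- Nordic renal: 28.84 / 28.10 = 1.026
- UK bladder 1.042; UK urinary tract 1.034

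At a difference of exactly 10%, varying the share of men from 50% to 65% moves the Nordic bladder factor only from 1.052 to 1.042.

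**Age at 9.9%.** Bias factor = (1 + slope)^(0.099 × SD).
- Low: 1.04^(0.099 × 9) = 1.036
- High: 1.08^(0.099 × 11) = 1.087

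**Both at the limit, same direction, urinary tract cancer.** 1.039 × 1.036 = 1.076 and 1.039 × 1.087 = 1.13, so about 8–13%.

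**Effect on the test.** SE(log HR) = ln(1.37) / (1.96 + 0.84) = 0.112. The two-sided rejection probability under the null is P(|Z + ln(bias)/SE| > 1.96).

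| Bias in urinary tract HR | Rejection under the null |
|---|---|
| none | 5% |
| 1.04 (sex alone) | 6.4% |
| 1.08 | 10.5% |
| 1.13 | 19.3% |

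For bladder cancer, SE = ln(1.47) / 2.80 = 0.138, and a factor of 1.045 gives 6.2%.

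**Do few events rule out two more terms?** The sparsest case is UK renal cancer. With 16,360 initiators matched 1:3, an incidence of 26.5 per 100,000 person-years and 2.4 − 0.5 = 1.9 years after the lag, the expected number under HR 1 is 65,440 × (1 − exp(−0.000265 × 1.9)) ≈ 33. Sex and linear age cost two terms.

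**The case against.** PS matching is the design's main control of confounding, and age and sex belong to it: protocol Table 4 and Annex 6 list them and SAP Table 11 feeds them to the PS. A reader might infer that they go unmatched. That is not so; they are not matched exactly.

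A reader might also infer that the SAP drops an exact-matching requirement. The documents do not support this. Table 4 lists options, the protocol abstract accepts exact or PS matching, footnote 4 sets the same balance-based rule, and protocol 8.7.1.5 says that matching variables enter the outcome model only after selection. In the text I worked from, the model-adjustment column is missing for the age and sex rows; a tick there would still fall under footnote 4.

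There are safeguards. SAP Table 16 plans HRs by age category, sex and PS quartile with meta-analyses, and SAP 6.6.2 foresees a narrower caliper if many covariates stay unbalanced. The combined 8–13% needs both variables at the limit, in the same direction, everywhere. The documents give no direction of channelling, and opposite imbalances would offset.

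All of this stands, and it removes any charge of deviation. It does not show that the 10% cut-off suits strong predictors. The stratified HRs can reveal a problem but do not correct the primary pooled estimate.

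**Conclusion.** Age and sex are balanced through PS matching only, and nothing in the SAP guarantees them a place in the PS model or the primary Cox models. The approach is prespecified and consistent with the protocol, so this is a free improvement, not an error.

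The part resting on documented rates is small: at most about 4.5% on the bladder HR and 4% on the urinary tract HR from sex, with type I error near 6%. Only the 60% share of men (and the 80% power behind the SE) is assumed. Table 1 describes the general population, so its sex ratio is taken to carry over to patients with type 2 diabetes. The age part, about 4–9%, rests wholly on assumed gradients. The combined 8–13%, with type I error of about 11% to just under 20%, is a worst case. Reading it as the bias to expect would go beyond the documents.

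The few-events argument in SAP change 8 explains why not every confounder can be modelled. It does not explain leaving out two or three terms.

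**What to change.** In SAP 6.5.1, state that age and sex are always in the PS model. In SAP 6.7.2, state that continuous age and sex are in every base and adjusted Cox model, for all three outcomes and for both the full and the metformin-user cohorts, whatever their standardized difference.

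Exempt both from the convergence-removal sequence. That sequence drops the covariate with the smallest standardized difference first, so well-balanced age and sex would be the first to go. Entering age as continuous also avoids losing a seven-category age variable to the rule of five events per category.

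Keep the 10% rule for all other covariates, including smoking. Smoking is only partly recorded in Finland, where it comes from AvoHILMO and the regional EMR databases (EMR coverage about 26.7%, protocol 8.9.2), and forcing it in would bring a missing-data category with it.

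The cost is a sentence in each section and two model terms, or slightly more if age is given a flexible form. Both variables are already collected, and no sample size or power assumption changes.

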6.7.3. META-ANALYSES

Meta-analyses will be carried out when there is no relevant heterogeneity of variable definitions and effect size of outcomes with respect to primary exposures among country-specific analyses. Country-level effect-sizes will be pooled using meta-analysis models to compute pooled effect-size estimates.

